7.3.2 Secondary Analyses

Standard descriptive methods (means, medians, variances and interquartile ranges for continuous variables and proportions for dichotomous variables) will be used to characterize sexual risk behaviors, alcohol and drug use, domestic violence and depression rates at each in-person study visit. Prevalence of HIV infection at enrollment will be estimated by the proportion of women testing HIV positive at enrollment. If p is the estimated prevalence then the standard error sqrt(p*(1-p)/N) quantifies the uncertainty of this estimate where N \approx 2,000. If the estimated prevalence is 5%, then a 95% CI for the true prevalence will have width \pm 1.96*0.005 = \pm 0.01.

Each woman in the study will be assigned a time of seroconversion as follows: i) prior to the window period defined by the laboratory algorithm (i.e. chronic infection); ii) within the window period defined by the laboratory algorithm (i.e. recent infection); iii) within the first 6 months of follow-up (documented seroconversion); iv) within months 7 - 12 of follow-up (documented seroconversion); v) negative and censored at month 6 or 12, as appropriate. Individuals in groups iii – v will be included in a discrete time proportional hazards model to identify which risk factors identified at enrollment, such as concurrency, injecting drug use, depression, etc. are associated with (and predictive of) seroconversion. With only 26 projected seroconversion events during follow-up, however, we acknowledge that such analyses will have relatively low power.

These data, as well as data from other HPTN and non-HPTN studies, will be used by the NL to optimize and validate an algorithm for identifying recent infections among HIV seropositive individuals. It is likely that the BED assay (31), other laboratory assays, and clinical data will be used in such an algorithm. We define the "sensitivity" of the algorithm as the probability that the algorithm defines an individual as recently infected (within some predefined window period, W) given that he or she is in fact recently infected. The "specificity" is the probability that an individual who is not recently infected is classified as not recent. Women who seroconvert during the longitudinal follow-up portion of this study will be used to validate the sensitivity of the algorithm (i.e. a high proportion of samples from women who seroconvert during the study should be classified as recently infected). Women who are seropositive at entry and contribute 6- and/or 12-month samples in the longitudinal follow-up will be used to validate the specificity of the algorithm (i.e. the samples collected at 6 and 12 months should be classified as not recent). Sensitivity and specificity will be estimated by simple proportions and exact methods will be used to generate CIs.

Finally, these data will be used to test the hypothesis

Ho:
$$I_r = I_f$$

Ha: $I_r \neq I_f$.

Effectively, this is testing whether or not the incidence observed in cross-sectional testing at study entry is similar to the incidence observed over follow-up. Assuming 42 total incident infections and 40% of the person-years from the cross-sectional incidence estimate versus 60% of the person-years from the longitudinal incidence estimate, we will have 80% power to detect a relative incidence (I_r / I_f) of 2.4.

Another important secondary analysis of these data will be to estimate the CV of incidence among the communities. The estimated CV is given by

$$CV = \frac{\sqrt{S^2 - I_p * \sum_j \left(\frac{M}{Y_j}\right)}}{I_p}$$

where S^2 is the observed variance in incidence across the M=10 communities and Y_j is the number of person-years from community j.(17) This information will be important in determining sample size for future intervention trials. Hughes(18) describes how baseline data such as these can be used to help inform the design of such trials.

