7 STATISTICAL CONSIDERATIONS

7.1 Review Of Study Design

The primary objective of this study is to estimate the overall HIV-1 incidence rate among 2,000 women in the US from defined geographic areas with high HIV prevalence and poverty. We will not attempt to precisely characterize HIV incidence rates within each community; rather, we will show that the proposed strategy for identifying women and communities will provide a precise estimate of HIV seroincidence across all ten communities.

This study will enroll 2,000 women at risk of HIV acquisition across 10 communities, including approximately 1,900 seronegative women and approximately 100 HIV seropositive women who have no reported history of past HIV diagnosis. Women who have a reactive HIV rapid test result will have samples sent to the HPTN NL for testing that includes the BED assay. Results from these tests will be combined with clinical data. to identify participants with recent HIV infection. Clinical data will likely include, but will not be limited to, the following: current/previous antiretroviral therapy, CD4 counts, etc. The multi-assay algorithm to define recent HIV infection based on cross-sectional testing will be defined and validated before it is used to generate HIV incidence estimates in ISIS. Participants will be followed for up to 12 months, with repeated collection of samples for HIV testing at 6 and 12 months. The 6- and 12-month HIV testing results will be used as follows:

Among those who are seronegative at study entry:

- To identify cases of incident HIV infection (traditional seroconversion analysis).
- To validate the "sensitivity" of the algorithm used for cross-sectional incidence testing.

Among those who are seropositive at study entry:

• To validate the "specificity" of the algorithm used for cross-sectional incidence testing.

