7.2 Accrual, Follow-Up, and Sample Size

For this study, the ISIS team will identify 10 communities from which women at risk of HIV acquisition will be recruited using criteria outlined in Section 3.1. Within each community, 200 women will be enrolled. Women enrolled in the first 3 months at each site will be followed for 12 months, while women enrolled in the next 3 months at each site (months 4 - 6) will be followed for 6 months. However, if accrual is slower than anticipated (i.e., if < 50% of the cohort is enrolled by month 3), we will extend the follow-up duration to 12 months for individuals enrolled in month 4

and, if needed, in month 5. We assume that approximately 5% of the enrolled cohort will be HIV seropositive at study entry. The HIV seronegative women will be followed for seroconversion; the HIV seropositive women will be followed to help determine whether they had recent versus non-recent HIV infection at enrollment, using a multi-assay laboratory algorithm for determination of HIV incidence. This will provide a total effective follow-up period for incidence calculations of ~220 person-years per community (about 40% from the enrollment visit based on a retrospective window period of 160 days, and 60% from the prospective longitudinal follow-up). A maximum of 10% loss-to-follow-up per year is assumed, yielding a total of ~210 person-years per community for analysis. Note that the estimated window period of 160 days is based on the BED assay, which is likely to be a major component of the multi-assay HIV incidence algorithm.

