Based on a recent infection window period of approximately 160 days, with a seropositivity rate of 5% and a seroincidence rate of 2%, the number of recently infected participants at enrollment is expected to be approximately 16. Assuming a similar seroincidence rate over the prospective follow-up period, and accounting for loss to follow-up, an additional 26 infections should be observed after enrollment (18 infections in months 1-6; 8 infections in months 7-12). Overall, this should yield approximately 42 incident infections. Assuming that a multi-assay algorithm for identifying recent infections is developed and validated at the HPTN NL in the near future, it will be possible to combine the cross-sectional HIV incidence estimate from enrollment with the longitudinal incidence estimate from follow-up into a single incidence estimate. Table 3 (below) gives the width of a 95% CI for the HIV incidence rate (pooling across communities) as a function of the total number of person-years in the feasibility study, assuming an underlying incidence of 2% per year and coefficient of variation (CV) in incidence across communities of 0.0 (we will, however, use the data from this study to estimate the CV – see Section 7.3.2). Once the multi-assay algorithm for identifying recent infections is validated, then the combined cross-sectional and longitudinal data will provide 2,000 – 2,200 person-years for incidence estimation and a 95% confidence interval (CI) of ± 0.0066 or less. An incidence estimate based only on the longitudinal (follow-up) data will include 1,200 – 1,300 person-years.

Person-years	800	1200	1600	2000	2400
CV = 0	± 0.010	0.0085	0.0074	0.0066	0.0060
CV = 0.1	± 0.010	0.0087	0.0075	0.0067	0.0061
CV = 0.2	± 0.011	0.0091	0.0080	0.0071	0.0065

 Table 3. Width of 95% CI for HIV-incidence based on total person-years of data, pooled across all communities

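### The planned between-community CV estimate is often undefined and cannot separate CVs of 0 to 0.2, so it needs a rule for negative values, an interval and a caveat

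*Protocol*

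**What the plan says.** Section 7.3.2 introduces the analysis with the words "Another important secondary analysis of these data will be to estimate the CV of incidence among the communities". It gives a closed formula in which S² "is the observed variance in incidence across the M=10 communities", a Poisson sampling term is subtracted, the square root is taken, and the result is divided by the pooled incidence. On its use it says "This information will be important in determining sample size for future intervention trials", and it cites a methods paper on using baseline data in trial design.

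The planning figures are in 7.2: "Overall, this should yield approximately 42 incident infections" and "yielding a total of ~210 person-years per community for analysis". The Table 3 precision calculation is introduced as "assuming an underlying incidence of 2% per year and coefficient of variation (CV) in incidence across communities of 0.0", and the table adds rows for CV 0.1 and 0.2. Section 7.1 states "We will not attempt to precisely characterize HIV incidence rates within each community".

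For the CV, 7.3.2 gives no rule for a negative value under the root, no measure of uncertainty and no caveat. Its other analyses are treated differently. Prevalence has a standard error and interval, sensitivity and specificity have exact intervals, the comparison of the two incidence estimates has a power figure, and the 26-event risk-factor model has a low-power warning.

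**The concern.** The CV is built from ten community rates that 7.1 says will not be precise, each resting on about four events. When sampling variance is much larger than between-community variance, a difference of variances on 9 degrees of freedom is often negative, and the printed rule then returns nothing. When the difference is positive, the root of a small noisy quantity can look like moderate heterogeneity that is not there.

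What is at stake is a later design with a community-level component, which Section 1.2.4 foresees as community testing campaigns for men. An undefined value read as zero would make such a trial too small. A chance value near 0.3 could arise from no true variation at all.

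As an illustration, assume 500 person-years per cluster (the protocol gives no such figure) and 2% incidence. The inflation 1 + CV² × I × Y is then 1.0 at CV 0, 1 + 0.04 × 10 = 1.4 at CV 0.2, and 1 + 0.36 × 10 = 4.6 at CV 0.6.

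**Working it through.** **Inputs.** M = 10 communities (7.3.2), about 210 person-years per community (7.2), and incidence 2% per year with CVs 0, 0.1 and 0.2 (7.2 and Table 3).

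**Reproducing the plan's event count.** 0.02 × 10 × 210 = 42.0, as stated. By component:
- At enrollment: 1,900 × 0.02 × 160/365 = 16.7 (the plan says "the number of recently infected participants at enrollment is expected to be approximately 16").
- Months 1 to 6: 1,900 × 0.5 × 0.02 × 0.95 = 18.05 (stated 18).
- Months 7 to 12: 950 × 0.5 × 0.02 × 0.90 = 8.55 (stated 8).

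The stated parts sum to 42, or 4.2 per community. The plan states no precision for the CV, so there is no such figure to reproduce.

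**Size of the signal.** Sampling variance of one community rate is 0.02/210 = 9.5 × 10⁻⁵. Between-community variance at CV 0.2 is (0.2 × 0.02)² = 1.6 × 10⁻⁵, about one sixth of it.

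**Probability of a negative difference.** The estimator examined is sqrt(S² − I_p × mean(1/Y_j))/I_p, with S² on divisor 9. This is the correct moment form. Whether the multiplier in the printed sampling term is right is a separate matter, possibly a text-extraction fault, and nothing here depends on it.

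Approximately, P(negative) = P(χ²₉ < 9/(1 + CV² × 0.02 × 210)):
- CV 0: P(χ²₉ < 9) = 56%.
- CV 0.1: P(χ²₉ < 9/1.042) = 53%.
- CV 0.2: P(χ²₉ < 9/1.168) = 44%.

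Simulation with 200,000 studies per scenario, gamma-distributed true rates and Poisson counts:

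| True CV | Undefined | Median when defined | 97.5th percentile (undefined = 0) |
|---|---|---|---|
| 0 | 56% | 0.28 | 0.52 |
| 0.1 | 53% | 0.29 | 0.54 |
| 0.2 | 44% | 0.31 | 0.60 |
| 0.3 | 32% | 0.36 | 0.69 |
| 0.4 | 21% | 0.41 | 0.79 |
| 0.5 | 13% | 0.48 | 0.91 |
| 1.0 | 1% | 0.87 | 1.57 |

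**Sensitivity.**
- Lognormal rates: 56% at CV 0 and 44% at CV 0.2.
- Person-years varying from 150 to 270: 56%, 53% and 44% at CV 0, 0.1 and 0.2.
- Incidence at CV 0.2: 50% undefined at 1% per year, 39% at 3%.
- Follow-up data only, the fallback in 7.3.1 if no algorithm is validated (1,200 to 1,300 person-years in all, so about 125 per community): about 57%, 55% and 49% at CV 0, 0.1 and 0.2.

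**What an interval would show.** Suppose the observed CV is 0.2. Then S² = 9.5 × 10⁻⁵ + 1.6 × 10⁻⁵ = 1.11 × 10⁻⁴. The upper chi-square limit is 9 × 1.11 × 10⁻⁴/2.70 = 3.71 × 10⁻⁴. Subtracting the sampling variance leaves 2.75 × 10⁻⁴, and the root divided by 0.02 is 0.83. The lower limit is 0. A simulated profile-likelihood interval from a gamma-Poisson model has a median upper limit of about 0.6 to 0.66 when the true CV is 0 to 0.2.

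**Would another point estimator help?** With equal person-years, the gamma-Poisson maximum-likelihood CV is zero whenever the divisor-10 variance does not exceed the Poisson variance. That happens in about 66%, 62% and 53% of studies at CV 0, 0.1 and 0.2, more often than the moment estimator fails.

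**The case against.** Several points on the other side stand.

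- A reader might infer that the estimate fails in about half of studies whatever the truth. It does not: that share holds only for CV 0 to 0.2. Table 3 shows those values in a precision calculation and does not call them the plausible range. The background stresses geographic variation (prevalence of 0.47% to 8.99% across 25 cities). That is prevalence, so it does not fix an incidence CV, but it gives no reason to cap the CV at 0.2.
- A reader might infer that the defined estimate is always too high. Its median is close to the truth at 0.4 and falls below it from about 0.5. The estimator can tell low from large heterogeneity.
- A reader might infer that later trials will be sized directly on this number. The text says only that the information will be important in determining sample size.
- Silence on an interval does not show that none will be reported, since a statistical analysis plan could supply it. The CV is also not a listed objective in 2.2, and the pooled primary estimate does not use it.

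These limit the point but do not remove it. The protocol itself fixes a formula that can return no value and names its purpose. It gives no warning about precision, while the same section warns about a 26-event model.

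**Conclusion.** The point holds in a conditional form. On the protocol's own inputs, the stated rule gives no value in about 44% to 56% of studies if the true CV is 0.2 or less. Its defined values centre on 0.28 to 0.31 whichever of those CVs is true. At larger CVs it becomes usable: about 13% undefined at 0.5 and 1% at 1.0.

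This assumes 2% incidence, about 210 person-years in each of 10 communities, Poisson counts and a correctly written sampling term. The result changes little with the rate distribution or moderately unequal person-years. It worsens at lower incidence or with follow-up data only.

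The primary incidence estimate is unaffected. The documents do not support a claim that a future trial will be wrongly sized. They support the narrower conclusion that the CV, as specified, is not fit to pass on as a bare point estimate. The change is worth making but is not critical to this study.

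**What to change.** In 7.3.2:

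1. Keep the moment estimator, with the sampling term written as I_p × (1/M) × Σ(1/Y_j), and set the CV to zero when the difference is negative.
2. Always report it with a 95% interval, either profile likelihood from a gamma-Poisson model of community infections with log person-years as offset, or a parametric bootstrap.
3. State that the interval or its upper limit, not the point estimate alone, informs future sample sizes.
4. Add a caveat like the one already given for the risk-factor model: if the true CV is 0.2 or less, the study is expected only to bound it, with a median upper limit of about 0.6 to 0.66.

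Replacing the point estimator with the gamma-Poisson maximum-likelihood value is not needed. The cost is a few lines of text and one extra model fit or bootstrap, with no new data. The drawback is that the reported CV will look less definite.

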7.3.3 Qualitative Analysis

Data collected during interviews and FGs will be analyzed using qualitative content analysis methods. Focus groups will be characterized based on demographics, risk behaviors and geographic distribution. Data analysis by the HPTN CORE will begin during data collection by transcribing and translating each recorded interview. As soon as possible after the interviews are conducted, transcript text will be read and re-read carefully by the Protocol Co-Chairs, CORE Manager and site PIs in order to (1) become familiar with the qualitative component; (2) identify text that may be unclear; (3) point out areas in which interviewing and transcription techniques could be improved; and (4) identify recurrent themes.

Timely analysis of the data will occur at multiple points throughout data collection in order to assess saturation and to provide ISIS research staff with preliminary data to inform the development of future interventions. For example, summary information will be provided on community characteristics and the economic hardships that women in ISIS communities may face. Summaries may also include participant (both male and female) views on HIV prevention strategies and participant perceptions of potential interventions. More in-depth analysis of the data will also be carried out, as described below. Final data cleaning and analysis should be conducted within two months after the end of data collection.

Data-derived codes developed through inductive coding and retrieving will be used. Codes for retrieving text for key concepts related to the overall objectives will also be applied to the data. The Protocol Co-Chairs, CORE Manager and site PIs will determine a coding frame to be used based on the first few interviews available for analysis. Appropriate software programs will be used to organize all qualitative data and prepare it for analysis. Input from community representatives will be obtained at specific intervals throughout the data analysis process to enhance the validity of the coding and analysis process. Procedures will be put into place to check for inter- and intra-site discrepancies as well as inter- and intra-coder reliability.

Discrepancies will be noted, discussed and resolved by the Protocol co-chairs, CORE Manager, and site investigators. The resolution of such discrepancies will be amended to the existing coding framework. Once all the transcripts have been coded, textual coding reports will be produced. Data display matrices will be developed to examine each code in detail for sub-themes and patterns across the interviews, followed by data reduction tables. Based on data analysis, specific themes will be identified that tie into the secondary study objectives, and recommendations will be made on strategies to enhance understanding of ISIS communities and the recruitment, retention and prevention strategies to reduce HIV acquisition in women in future trials.

7.4 Interim Monitoring

There will be no interim efficacy analysis or stopping criteria for this study.

8 HUMAN PARTICIPANTS CONSIDERATIONS

8.1 Ethical Review

This protocol and the template informed consent forms contained in Appendices II-VIII — and any subsequent amendments — will be reviewed and approved by DAIDS Prevention Science Review Committee (PSRC) with respect to scientific content and compliance with applicable research and human subjects regulations.

The protocol, site-specific informed consent forms, participant education and recruitment materials, and other requested documents, and any subsequent modifications, will be reviewed and approved by the ethical review bodies responsible for oversight of research conducted at each study site. For sites intending to utilize verbal consent for screening, a waiver of written consent must be obtained from their Institutional Review Boards/Ethical Committees (IRBs/ECs)for this procedure.

Subsequent to initial review and approval, the responsible local IRBs/ECs will review the protocol at least annually. The Investigator will make safety and progress reports to the IRBs/ECs at least annually, and within three months of study termination or completion. These reports will include the total number of participants enrolled in the study, the number of participants who completed the study, all changes in the research activity, and all unanticipated problems involving risks to human participants or others.

8.2 Informed Consent

Informed consent will be obtained from each study participant. No study procedures will take place prior to informed consent. Each study site is responsible for adapting study template forms for local use based on the templates in Appendices II-VIII, that describe the purpose of the study, the procedures to be followed, and the risks and benefits of participation, and an optional consent for storage and future use of blood for research purposes, as well as the qualitative components of the study and other than protocol-related testing in accordance with all applicable local and US regulations. The templates in Appendices IV-VII apply only to sites participating in the qualitative component of ISIS. Sites may choose to combine consent forms (e.g. combined written informed consent prior to screening, and must adapt the templates in the Appendices accordingly. However, written informed consent must be obtained prior to study enrollment. Each study site will consult with a local

community advisory board to understand concerns about the study, potential misunderstandings about the study by eligible participants, challenges in the informed consent process, and ways to strengthen the informed consent process. An additional informed consent will be developed to include Health Insurance Portability and Accountability Act (HIPAA) regulations (Appendix VIII). Sites may adapt the protocol template or preexisting site HIPPA forms. The study site is responsible for translating the template forms into Spanish if applicable, checking that the consent process and language is culturally appropriate, and verifying the accuracy of the translation by performing an independent back-translation. In addition, the consent form will be targeted to a Grade 6 reading level.

Before documenting their informed consent, participants will be given the opportunity to ask questions. They will be told that they can return at any time to obtain more information or have further questions answered. Participants will be offered a copy of their informed consent forms. Study staff will document the informed consent process as instructed in the SSP manual.

